7.1.1 Primary objective

The primary objective of this study is to confirm safety of the BIOMONITOR III system by recording and evaluating all Serious Adverse Device Effects (SADEs) related to the BIOMONITOR III, the Incision and FIT OneStep Insertion Tool and the insertion procedure until 3 months.

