7.2 Endpoints and hypotheses

7.2.1 Primary endpoint and hypothesis

SADE-free rate until the 3-month follow-up

A primary endpoint is an SADE (see definition in section 18) that is possibly, probably or causally related to the BIOMONITOR III, the Incision Tool or the Insertion Tool, or the insertion procedure, which occurs before the 3-month follow-up.

SADEs will be adjudicated by an internal adjudication board, whereby the seriousness and device relatedness will be re-examined. If any amply documented external physical influence (e.g. accident, sport) or medical AE caused the SADE, it does not contribute to this endpoint. SADEs that occur later than the 3-month follow-up, and SADEs with onset date later than 105 days after insertion procedure (3 months defined as 91 days after implantation + 14 days would still be in accordance to the CIP) in case the 3-month follow-up was not conducted or conducted outside the specified time interval, do not contribute to this endpoint.

The parameter of interest p_{SADE} is the SADE free rate, which will be calculated by

$$1 - \frac{\text{Number of patients with one or more primary endpoint until the 3 months FU}}{\text{Number of patients at the 3 months FU or with primary endpoint}}$$

in percent. The period of observation starts with the insertion of the BIOMONITOR III and takes until the 3-month follow-up.

It is expected, that the SADE-free rate will be significantly above 90%. Therefore the corresponding hypotheses definitions are:

Null hypothesis:

$$H_0 : p_{SADE} \leq 90\%$$

Alternative hypothesis:

$$H_A : p_{SADE} > 90\%$$

The following patients are not included in the analysis set for this endpoint:

- Patients without SADE, prematurely terminated before the time window for the 3-month follow-up, i.e. less than 77 days after insertion procedure (3 months defined as 91 days after implantation – 14 days would still be in accordance to the CIP).

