18.1 Definition of adverse events

An AE is defined* as any untoward medical occurrence, unintended disease or injury, or untoward clinical signs (including abnormal laboratory findings) in subjects, users or other persons whether or not related to the investigational device. This includes:

- Events related to the investigational device or the comparator
- Events related to the procedures involved
- For users or other persons, this definition is restricted to events related to the investigational devices.

Symptoms of the **known diseases** of the subject, like syncope with uncertain origin or atrial fibrillation, which were present already before participation in the study and do not change in frequency or severity during the course of the study are **no AE**. Also **planned** subsequent processing, like BIOMONITOR III explantation, implantation of a pacemaker, ICD or CRT device, or ablation, are **no AE**.

*see ISO 14155 3.2

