18.2.1 Causality Assessment

The relationship between the use of the investigational device (including the medical-surgical procedure) and the occurrence of each adverse event shall be assessed and categorized, considering the presence of confounding factors, such as concomitant medication and treatment, the natural history of the underlying disease, other concurrent illness or risk factors.

Each AE will be classified according to five different levels of causality. As defined in the Meddev 2.7/3 rev 3, the investigator will use the following definitions to assess the relationship of the serious adverse event to the investigational device or procedures and the sponsor will review the investigator's categorization:

Not related: the relationship to the device or procedures can be excluded.

Unlikely: the relationship with the use of the device seems not relevant and/or the event can be reasonably explained by another cause, but additional information may be obtained.

Possible: the relationship with the use of the investigational device is weak but cannot be ruled out completely. Alternative causes are also possible (e.g. an underlying or concurrent

illness/clinical condition or/and an effect of another device, drug or treatment). Cases were relatedness cannot be assessed or no information has been obtained should also be classified as possible.

Probable: the relationship with the use of the investigational device seems relevant and/or the event cannot be reasonably explained by another cause, but additional information may be obtained.

Causal relationship: the serious event is associated with the investigational device or with device procedures without reasonable doubt.

The investigators will distinguish between adverse events related to the investigational device and those related to the device procedures (any procedure specific to the investigational device). Procedure related events refer to the procedure related to the application of the investigational device only and therefore not to any other procedure for other devices and not to any other procedures or treatments applied later throughout the clinical investigation, for instance to treat (serious) adverse events. In case of a replacement of the investigational device in response to an adverse event (e.g. lead replacement after dislocation), the replacement will be considered like an initial application of a new investigational device and shall be assessed accordingly.

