18.8 Reporting responsibilities

18.8.1 Reporting responsibilities of the investigator to sponsor

The investigator shall document all events on the respective eCRF pages provided within the CDMS. The indicated timelines for reporting of initial cases and possible update reports shall be strictly followed (see section 18.9).

All AEs and ADEs) shall be reported together with an assessment by completing the AE-CRF in accordance with ISO 14155:2011.

For device deficiencies of the investigational device, a DD-CRF shall be completed.

The reports shall be done with all information available, even if this results in an incomplete report. The investigator has to follow-up ongoing Events either as long as the patient participates in the study, the clinical investigation is terminated prematurely or until the event has been resolved, whatever comes first. Ongoing SADEs related to the investigational device will be followed for a maximum time period of either 4 weeks after pre-mature or regular study termination of the individual patient. This also applies to Adverse Events involving the explantation or replacement of an investigational device, heart transplantation or implantation of a ventricular assist device. This follow-up period is reduced if 'Last Patient Out' is announced in the study. All follow-ups on open adverse events will stop at this point in time at the latest.

Multiple events may occur simultaneously in one subject. For each medically independent event an individual report must be provided.

In addition, the action taken/treatment should also be provided with any supportive documentation available.

The investigator has to ensure that all relevant information is available. This also includes information from other parties (family, other hospitals etc.).

If a patient dies during the study this might be subject to special reporting requirements in some countries. Therefore as much information as possible should be provided to enable BIOTRONIK to explain the circumstances leading to death. At least a pseudomized copy of the death records and an autopsy report (if performed) should be sent to BIOTRONIK promptly. All actions taken, which were initiated to gain further information must be documented in writing and provided to BIOTRONIK.

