## 10. Primary Endpoint1

### CIP chapter 7.2.1 - Primary endpoint and hypothesis

SADE-free rate until the 3-month follow-up

A primary endpoint is an SADE (see definition in section 18) that is possibly, probably or causally related to the BIOMONITOR III, the Incision Tool or the Insertion Tool, or the insertion procedure, which occurs before the 3-month follow-up.

SADEs will be adjudicated by an internal adjudication board, whereby the seriousness and device relatedness will be re-examined. If any amply documented external physical influence (e.g. accident, sport) or medical AE caused the SADE, it does not contribute to this endpoint. SADEs that occur later than the 3-month follow-up, and SADEs with onset date later than 105 days after insertion procedure (3 months defined as 91 days after implantation + 14 days would still be in accordance to the CIP) in case the 3-month follow-up was not conducted or conducted outside the specified time interval, do not contribute to this endpoint.

The parameter of interest is the SADE free rate, which will be calculated by

$$\frac{\text{Number of patients with one or more primary endpoint until the 3 months FU}}{\text{Number of patients at the 3 months FU or with primary endpoint}}$$

$$\text{in percent. The period of observation starts with the insertion of the BIOMONITOR III and takes until the 3-month follow-up.}$$

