### 10.1. Analysis set

The number of patients with at least one primary endpoint until the 3 months FU (the numerator) will be determined by assessing the variable "AERELPET" in the "AE evaluation" form. This form is filled by the AE evaluation board and the variable "AERELPET" is set to "Yes" if and only if all conditions defined in 7.2.1 in the CIP are met.

The denominator will be calculated as follows:

1. The number of patients with 3 months FU will be counted by the number of non-missing entries in SVSTDT in the "3 month FU" form.
2. The number of patients with primary endpoint will be calculated as defined above.
3. In case of patients lying in the intersection of both sets, these patients will be counted once.
4. Patients without SADE and termination date less than 77 days after insertion will be disregarded.

Patients who do not attend the 3 months FU, but who have not terminated study participation earlier than 77 days after insertion will be included in the analysis.

For the calculation of the Kaplan-Meier analysis, the following time variables will be used:

1. For patients with at least one primary endpoint: time from insertion to time of first primary endpoint [REDACTED]
2. For patients without primary endpoint: time from insertion to last information available [REDACTED]

For the KM analysis data of all patients is used.

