## 10.2. Variables

| Data file, identifier patient_display_id_full | Notes   | Variable name                    | Variable label                                 | Variable level | Nominal values |
|---|---|----------------------------------|--|----------------|----------------|
| AE evaluation                                 | sorted by patient_display_id_full and AESTDT and removed duplicates | AERELPET                         | Adverse event is relevant for primary endpoint | nominal        | Yes
No      |
| 3-month FU                                    |   | SVSTDT                           | Date of visit                                  | date           |                |
| 3-month FU                                    |   | sar_3mFU_available  | 3m FU available?                               | nominal        | Yes
No      |
| Termination                                   |   | sar_term_77         | Termination less than 77 days after insertion? | nominal        | Yes
No      |

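### Could the medical-AE exclusion in the primary endpoint remove device- or procedure-related SADEs and inflate the SADE-free rate?

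*Protocol*

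**What the plan says.** Section 7.2.1 of the protocol defines a primary endpoint event as an SADE possibly, probably or causally related to the BIOMONITOR III, the incision or insertion tool, or the insertion procedure, before the 3-month follow-up. An internal board re-examines seriousness and device relatedness. The exclusion follows directly: "If any amply documented external physical influence (e.g. accident, sport) or medical AE caused the SADE, it does not contribute to this endpoint". SAP section 10 copies it ("or medical AE caused the SADE, it does not contribute to this endpoint").

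SAP 10.1 takes the numerator from the variable AERELPET, labelled in SAP 10.2 "Adverse event is relevant for primary endpoint". The board sets it to Yes "if and only if all conditions defined in 7.2.1 in the CIP are met".

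Four other parts of the protocol bear on the point:

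- The primary objective (7.1.1) is to confirm safety by "recording and evaluating all Serious Adverse Device Effects (SADEs) related to the BIOMONITOR III", the tools and the procedure.
- The AE definition (18.1) covers related as well as unrelated events, including "Events related to the procedures involved".
- Under 18.2.1, "Each AE will be classified according to five different levels of causality".
- Under 18.8.1, "For each medically independent event an individual report must be provided".

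**The concern.** Read alone, the exclusion sentence has no qualifier. Every undesired medical event is an AE under section 18, including an insertion-site infection or hematoma, so the word medical does not narrow the rule. If such an event were reported first and a serious complication of it were reported separately, the second event could be said to have been caused by a medical AE and be flagged No. That would contradict the objective of evaluating all related SADEs.

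The setting makes this worth checking. The study has a single arm, a fixed 90% threshold and one confirmatory test, the board is internal, and there is no data monitoring committee. The exclusion can only lower the event count. No planned analysis recomputes the rate with the removed events put back; the with/without provision in SAP 5.4 concerns unresolved spurious data. If related SADEs were dropped, the SADE-free rate would be too high and a failed test could become a pass.

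**Working it through.** **The plan's own figures.** Inputs from protocol 7.2.1, 11.2 and 11.3: null rate 0.90, expected rate 0.97, one-sided alpha 0.025, power 0.90, drop-out 10%.

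- Normal approximation: n = [(1.960 × √(0.90 × 0.10) + 1.282 × √(0.97 × 0.03)) / 0.07]² = 132.8, so 133; 133 / 0.9 = 147.8, so 148.
- Exact binomial: power stays above 90% from n = 141 (93.7%); 141 / 0.9 = 156.7, so 157.

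Both agree with section 11.2.

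**Decision limit.** Let X be the number of patients with an endpoint event. Under the null, X is binomial with rate 0.10.

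| n | X | p = P(X or fewer) | Result |
|---|---|---|---|
| 141 | 7 | 0.0242 | pass |
| 141 | 8 | 0.0502 | fail |
| 157 | 8 | 0.0207 | pass |
| 157 | 9 | 0.0420 | fail |

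At n = 141, removing one patient's event changes the verdict only if exactly 8 patients had one and that patient stays in the denominator. If the patient also leaves the denominator, 7 of 140 gives p = 0.0257, still a fail.

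**How often that happens.** P(X = 8) at n = 141 is 3.6% at the planned event rate of 3%. At the predecessor rates it is 2.1% for 4/152 (protocol 5.2.1, taking the 4 SADEs as 4 patients, over one year rather than 3 months) and 0.9% for 2/90 (5.2.4, inserted patients).

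**If a share f of event patients were removed.** The documents give no value for f, so these are illustrations. The chance of passing is P(X ≤ 7) at n = 141 with event rate q(1 − f).

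| True SADE-free rate | f = 0 | f = 10% | f = 20% | f = 30% |
|---|---|---|---|---|
| 97% | 93.7% | 96.2% | 97.9% | 99.0% |
| 90% | 2.4% | 5.5% | 11.6% | 22.2% |

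The lower row would be serious if f were that large for related events. The question is therefore whether the rule can remove patients with related SADEs at all.

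**Following one case through the definitions.** Suppose related AE A (say an insertion-site hematoma) causes SADE B within the window, and the board removes B because A is a medical AE.

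1. Under 18.4 an AE is serious if it led to one of the listed outcomes. A led to B's serious outcome, so A is serious.
2. Under 18.5 an adverse device effect with such consequences is an SADE. A is related, so A is an SADE.
3. A began before B. A related event cannot precede the insertion that starts the observation period, so A also lies in the window.
4. If A was in turn caused by an earlier related AE, steps 1 to 3 apply to that event. The first related event in the chain has no related AE behind it and counts.
5. Section 7.2.1 counts patients with one or more primary endpoints, and SAP 10.1 counts each patient once. The flag moves from B to A and the patient stays in the numerator.

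The binomial count is therefore unchanged; in the Kaplan-Meier display the event time would move to A's earlier onset. If the chain starts with an unrelated illness, the exclusion does what it was written to do.

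**The case for a change.** The strongest reply is that the rule behind the only pass/fail criterion should be unambiguous as written. The accident and sport examples attach to the external influence, not to the medical AE. Because SAP 10.1 ties the flag to the literal conditions of 7.2.1, the wording governs, whatever its authors intended. An internal board in an open-label study is a reason for tighter text. The argument from 18.4 and 18.5 also depends on the board recognising the causing AE as serious; if it called that AE related but non-serious and still removed the later SADE, the patient would be lost from the numerator.

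The missing qualifier and the possibility of such an inconsistent adjudication both stand. But that outcome needs the board to apply 7.2.1 literally while ignoring the seriousness definition, and the context runs the other way. The exclusion follows the board's review of relatedness, it requires ample documentation, and the protocol has its own term, adverse device effect, for related events, which the exclusion does not use. One report per medically independent event makes it likely that a worsening wound problem is recorded as a single SADE. Section 7.4 also refers to sponsor SOPs, not available here, which may settle the term.

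A supportive test that ignored the exclusion would leave the confirmatory result unchanged and would mainly add back accidents and unrelated illness that the protocol leaves out on purpose. All AEs are summarised in any case (protocol 7.4, SAP section 15), although those summaries do not promise to label the events removed under this rule.

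**Conclusion.** The wording is loose, but no bias in the SADE-free rate is shown and no change to the plan is needed. Under the plan's own definitions of seriousness and SADE, and with patients as the counting unit, a patient whose SADE arose from a related AE normally stays in the numerator. Writing in a qualifier would record what the board would be expected to do already; primary test, alpha and sample size would be the same with or without it.

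The effect on the verdict is small in any case. One removed patient matters only at exactly 8 events in 141, with probability 3.6% at the planned rate and 0.9% to 2.1% at the predecessor rates. The larger changes in the chance of passing rest on assumed removal shares of 10% to 30%, for which the documents offer no basis.

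This conclusion assumes that the board applies 18.4 and 18.5 consistently to the causing AE and reads the exclusion as covering causes other than the device, tools and procedure.

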11.2 Sample size

The sample size is calculated with the power procedure of SAS and is based on the primary endpoint (SADE-free rate).

An SADE-free rate of 97% is expected. With alpha = 2.5%, power = 90% and a one-sided hypothesis a sample size of n = 133 results (normal approximation). Taking into account a drop-out rate of 10% a preliminary sample size of n = 148 patients results. By assessing the sawtooth-shaped power curve (which is not monotonically increasing) for binomially distributed parameters the minimal sample size with power > 90% is 141 patients. Taking the 10% drop-out rate into account, a total sample size of n = 157 patients results.

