11.12 Exclusion of data from confirmatory data analysis

In the following cases, data are to be excluded from analysis of the primary endpoint:

- No data are allowed to be collected and included in the absence of a documented consent.
- Data of patients will be excluded from analysis in case a patient terminates the study prior to any insertion attempt.
- Patients without primary endpoint but premature study termination earlier than 77 days after insertion (91 days = 3 month minus 14 days tolerance) are not included in the analysis set to avoid an over-estimation of the SADE-free rate.
- Any event that occurred later than the pre-specified time window for the 3-month follow-up in patients who did not have a 3-month follow-up (91 days plus 14 days tolerance = 105 days) does not contribute to the primary endpoint.
- SADEs will be adjudicated by an internal adjudication board, whereby the investigator assessment of seriousness and device relatedness will be re-examined.

Details are provided in the Statistical Analysis Plan.

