## 5.5. Exclusion of data from confirmatory data analysis

*CIP chapter 11.12 Exclusion of data from the confirmatory data analysis*

*In the following cases, data are to be excluded from analysis of the primary endpoint:*

- *No data are allowed to be collected and included in the absence of a documented consent.*
- *Data of patients will be excluded from analysis in case a patient terminates the study prior to any insertion attempt.*

- Patients without primary endpoint but premature study termination earlier than 77 days after insertion (91 days = 3 month minus 14 days tolerance) are not included in the analysis set to avoid an over-estimation of the SADE-free rate.
- Any event that occurred later than the pre-specified time window for the 3-month follow-up in patients who did not have a 3-month follow-up (91 days plus 14 days tolerance = 105 days) does not contribute to the primary endpoint.
- SADEs will be adjudicated by an internal adjudication board, whereby the investigator assessment of seriousness and device relatedness will be re-examined.

The analysis will use all data that are stored in the study database. It is in the responsibility of the persons entering data and of those checking data before the final data export that the data comply with the approval of the patient.

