## 10.4. Hypotheses & Statistical Tests

Null hypothesis:

$$H_0 : p_{SADE} \leq 90\%$$

Alternative hypothesis:

$$H_A : p_{SADE} > 90\%$$

The hypothesis will be tested by using an exact binomial test against the value of 0.9. An exact two-sided confidence interval for the SADE-free rate.

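### The primary at-risk period ends at each patient's own 3-month visit (day 77 to 105 if compliant), so visit scheduling decides whether a SADE near the boundary counts; one fixed day is needed.

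*Protocol*

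**What the plan says.** CIP 7.2.1 defines a primary endpoint as a related SADE before the 3-month follow-up and runs observation from insertion to that visit. It then removes "SADEs that occur later than the 3-month follow-up, and SADEs with onset date later than 105 days after insertion procedure". The day-105 limit applies where the visit was not held or was held outside its interval. Three months is set at 91 days and the visit tolerance is 14 days either way, so a compliant visit falls between day 77 and day 105. SAP section 10 copies this text.

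SAP 10.1 has the evaluation board set AERELPET to yes only when every condition in CIP 7.2.1 is met. Patients who miss the visit but did not terminate before day 77 stay in the analysis. SAP 10.3 adds a Kaplan-Meier estimate at day 90.

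CIP 11.12, copied in SAP 5.5, lists exclusions. It says that an event after the visit window, "in patients who did not have a 3-month follow-up (91 days plus 14 days tolerance = 105 days"), "does not contribute to the primary endpoint". It is silent on visits that took place late. CIP 9.1 foresees such visits: a follow-up that misses its window is still to be performed.

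**The concern.** In a single-arm study with one confirmatory proportion, every patient should be at risk over the same period. Here the period differs by up to 105 - 77 = 28 days between fully compliant patients, and clinic scheduling sets it. Patients who skip the visit are observed longer than almost all who attend. The reported 3-month rate is then not the rate at any one time, and an event near the boundary is classified by appointment date.

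The planned Kaplan-Meier analysis might seem to repair this, but it does so only if its events are taken independently of AERELPET. If it uses that flag, a patient with a SADE on day 85 after a visit on day 80 appears event-free at day 90.

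**Working it through.** **1. The plan's own figures.** Inputs from CIP 11.2 and SAP 10.4: "An SADE-free rate of 97% is expected"; "The hypothesis will be tested by using an exact binomial test against the value of 0.9"; one-sided alpha 0.025; power 90%.

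- Normal approximation: n = [(1.960 × √(0.9 × 0.1) + 1.282 × √(0.97 × 0.03)) / 0.07]² = [(0.588 + 0.219) / 0.07]² = 132.8, so 133, as stated.
- Exact binomial at n = 141: success needs at most 7 SADE patients, with attained alpha 0.0242 and power 93.7%. Sizes 127 to 130 also exceed 90%, but 131 to 140 do not. From 141 power stays above 90% (checked to 164), so 141 is a sound reading of the sawtooth curve.
- Drop-out: 133 / 0.9 gives 148 and 141 / 0.9 gives 157, as stated.

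The sample size reproduces in full and is not in question.

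**2. The rules applied to example patients.**

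| SADE onset | 3-month visit | CIP 7.2.1 | CIP 11.12 / SAP 5.5 |
|---|---|---|---|
| Day 85 | Day 100 | counts | not excluded |
| Day 85 | Day 80 | does not count | not excluded |
| Day 85 | none, still in study | counts (limit day 105) | not excluded |
| Day 110 | none | does not count | excluded |
| Day 110 | Day 120 (late) | does not count | silent |
| Day 85 | Day 70 (early) | unclear | silent |

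The first three rows are the point: same event, same day, different result. In the last row the first clause of 7.2.1 would drop the event, and the text does not say whether the day-105 limit replaces that clause when the visit is too early.

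**3. Size.** The documents give no hazard shape, so these are assumptions: 97% SADE-free at day 91, with S(t) = 0.97^((t/91)^k). Here k = 1 is constant hazard and k < 1 is front-loaded. The table shows the rate if everyone were observed to the given day, with n = 141.

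| k | SADE-free, day 77 | SADE-free, day 105 | Expected SADE patients, day 77 vs 105 | Power, day 77 vs 105 |
|---|---|---|---|---|
| 1 | 97.46% | 96.55% | 3.6 vs 4.9 | 97.2% vs 88.4% |
| 0.5 | 97.24% | 96.78% | 3.9 vs 4.5 | 95.7% vs 91.4% |
| 0.25 | 97.12% | 96.89% | 4.1 vs 4.4 | 94.8% vs 92.6% |

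At day 91 power is 93.7% in every row, by construction. The two days are the extremes; a real mix of visit days lies between them.

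**4. Decision boundary at n = 141.** Seven SADE patients give p = 0.0242 (pass); eight give p = 0.0502 (fail). The expected number at 3% is 0.03 × 141 = 4.2.

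**The case against.** The best defence is that a cutoff tied to the visit is deliberate. Adverse events are actively checked at the visit, and none is scheduled between month 3 and month 12. Visits spread evenly over the window would average day 91, which is the CIP's own 3 months. CIP 5.3 expects most complications early, so few events fall between day 77 and day 105. All of this stands, and it limits the size. It does not remove the unequal treatment of identical events.

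It is also said that post-visit SADEs still reach the adverse event summaries and the 12-month rate. The first is true. The second is less certain, because SAP 14.2 lists the same AERELPET flag for the 12-month endpoint.

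Four stronger readings are tempting and are not supported:

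- *CIP 7.2.1 and 11.12 conflict, so a day-110 SADE before a day-120 visit would count under 11.12.* Section 11.12 only lists exclusions and does not say that such an event counts. Section 7.2.1 excludes it, and SAP 10.1 makes 7.2.1 decisive for the flag. This is a wording mismatch.
- *At-risk periods run beyond day 105.* That needs 11.12 read alone; 7.2.1 caps missed and late visits at day 105.
- *Observation is on average 14 days short.* That holds only against day 105, which is the end of the tolerance. Against day 91, evenly spread visits have no average shortfall.
- *One event decides the trial.* Only at 7 versus 8. Even against day 105, with a 3% event rate by then and visits spread evenly over the window, the chance that dropped events turn a fail into a pass is about 3.1% if event timing is uniform, and about 1.0% if 80% of events fall in the first 30 days.

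**Conclusion.** The concern holds as a defect of endpoint definition. The primary at-risk period ends on a patient-specific day between 77 and 105, so a SADE near the boundary counts or not according to the visit date. The Kaplan-Meier estimate inherits this if it uses AERELPET.

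The likely effect is small. Between the extremes of the window, the expected number of SADE patients in 141 differs by about 1.3 under constant hazard (4.9 - 3.6) and by about 0.3 under the most front-loaded case shown (4.4 - 4.1). These figures assume 97% SADE-free at day 91 and hazard shapes that the documents do not give. A reader should not infer a sample-size error, an alpha error, or two competing operative rules. The change is still worth making, because this is the only confirmatory endpoint and the correction is cheap.

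**What to change.** Define the primary endpoint as SADE onset from insertion through one fixed day for every patient, whether or not and whenever the 3-month visit took place. Day 91 matches the CIP's definition of 3 months and leaves power at 93.7% at n = 141 if 97% holds at that day. If day 105 is preferred, restate the power: 88.4% at n = 141 under constant hazard, below the planned 90%.

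- Use the same day in CIP 7.2.1, CIP 11.12, SAP 5.5, the AERELPET instruction in SAP 10.1 and the Kaplan-Meier time point in SAP 10.3 (now day 90).
- State how event-free patients who terminate between day 77 and the cutoff are handled, for example kept in the binomial denominator and censored in the Kaplan-Meier analysis. A fixed day alone does not equalise their exposure.
- Align CIP 11.12 and SAP 5.5 with 7.2.1 on late visits. A fixed day also settles visits before day 77.

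The onset dates are already collected: participation runs to month 12 (CIP 8.3.6) and serious events are reportable between visits (CIP 18.9).

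The cost is mainly wording. The interim data cut must wait until the last patient reaches the fixed day, at most 14 days after a day-77 visit for day 91 or 28 days for day 105. Onset between an early visit and the cutoff rests on continuous rather than visit-based reporting. The SADE-free rate may be slightly less favourable, most clearly with day 105, where it can only stay the same or fall.
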